### ***Assessing Randomization Success***

Randomization should ensure that no differences are found at baseline between the two conditions. However, the CM and Co groups will compared on core baseline measures (demographics and medical and mental health history) using *t*-tests for continuous and chi-square analyses for categorical variables to ensure no differences occurred by chance on important measures.

### ***Outcome Measures***

As shown in Table 4, the primary outcome measures are the number of completed daily self-monitoring surveys and the longest period of sustained adherence to survey completion. It is hypothesized that those in the CM group will complete more daily self-monitoring surveys and have a longer sustained period of daily survey completion compared to controls. The number of completed daily surveys and duration of continuous daily survey completion will be compared between CM and Co groups using independent *t*-tests.

Secondarily, descriptive statistics will be used to summarize CM participants' self-report of the impact of behavioral incentives on adherence. Mean time to complete the daily surveys between CM and Co groups will be compared using an independent *t*-test. Pain experience and

related variables from baseline will be compared to follow up responses for the total sample using paired *t*-tests. The daily survey item responses will be summarized for the overall sample using descriptive statistics. Associations between daily survey and follow-up TFLB for alcohol and prescription opioid use data for the overall sample and each study group will be examined using Spearman's correlations. Descriptive statistics will be used to summarize self-report validity and accuracy of responses. Feasibility and acceptability of CM app implementation will be examined by comparing follow-up acceptability survey ratings for each group using independent *t*-tests.

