## Introduction

The opioid epidemic has spurred urgent and widespread legal, medical, and behavioral approaches to promote effective opioid prescribing. Between 21-29% of chronic pain patients misuse prescription (Rx) opioids (Vowles et al., 2015). Responsible opioid prescribing depends on accurate and early identification of misuse as well as comprehensive understanding of predictors of pain treatment seeking and successful pain management (Dowell et al., 2016). One promising and practical pain management solution is remote self-monitoring, a state-of-the-art assessment tool shown to be superior to retrospective assessment (e.g., Heron & Smyth, 2010). Unfortunately, low rates of adherence have impeded the use of remote self-monitoring among chronic pain patients (e.g., Jamison et al., 2016), even when non-monetary rewards were included (Jamison et al., 2017). One robust strategy for improving adherence is contingency management (CM). While CM has been widely used in research, translation to clinical practice has been limited, due to practical barriers (e.g., costs) and counselor concerns (e.g., Polak et al., 2020; Carroll, 2014).

This Stage 1 behavioral therapies development project (Rounsaville et al., 2001) will pilot test a novel, fully automated CM app (DynamiCare Rewards) for promoting daily self-monitoring of pain symptom severity and related variables (e.g., sleep, mood), as well as Rx opioid and alcohol use in a sample of chronic pain patients. This study is the first to customize the DynamiCare Rewards app to target survey completion, followed by a pilot controlled trial, comparing participants randomized to receive CM for completing daily self-monitoring surveys (CM group) or receive only electronic daily reminders to complete the survey (control group) over a 28-day period. Primary outcome measures include number of daily surveys completed and longest period of sustained adherence to survey completion. The study tested the hypothesis

that CM group participants will complete more daily self-monitoring surveys and will have a longer sustained period of daily survey completion compared to control group participants. Secondarily, the study examined feasibility; acceptability; and accuracy of Rx opioid and alcohol use reporting.

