## **Aims**

The specific aims of this Phase 1 therapy development project are to:

*Aim 1:* Compare number of completed daily self-monitoring surveys in CM and C groups. One hypothesis was tested:

*Hypothesis 1:* CM group participants will complete more daily self-monitoring surveys compared to control group participants.

*Aim 2:* Compare longest sustained period of daily survey completion in CM and C groups. One hypothesis was tested:

*Hypothesis 1:* CM group participants will have a longer sustained period of daily survey completion compared to control group participants.

*Aim 3:* Examine agreement between daily survey and follow-up visit reports of alcohol and Rx opioid use in CM and C groups.

*Aim 4:* Examine feasibility and acceptability of CM app implementation targeting self-monitoring of pain severity, related factors, and use of Rx opioids and alcohol.

*Aim 5:* Estimate effect-size to be used to perform power analyses and sample size calculations as part of the design of a larger RCT.

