## **Data Analysis Plan**

### ***Effect Size Estimation***

The major goal of this Stage I pilot RCT is to estimate the effect size of the primary outcome variables (Rounsville et al., 2001). This will be done by using the means and variances of the CM and Co groups on the primary outcome variables. This estimated effect-size will then be used to perform power analyses and sample size calculations to be used in the design of a larger clinical trial.

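### Is the primary hypothesis one joint claim or two separate claims, and would a split result leave the conclusion undefined?

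*Combined protocol and SAP*

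**What the plan says.** The Introduction uses the singular, "The study tested the hypothesis", and continues "that CM group participants will complete more daily self-monitoring surveys and will have a longer sustained period of daily survey completion". The Outcome Measures section of the Data Analysis Plan repeats this as one sentence: "It is hypothesized that those in the CM group will complete more daily self-monitoring surveys and have a longer sustained period".

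The Aims section separates the outcomes. Aim 1 reads "Compare number of completed daily self-monitoring surveys in CM and C groups. One hypothesis was tested" and Aim 2 reads "Compare longest sustained period of daily survey completion in CM and C groups. One hypothesis was tested". Each is followed by its own Hypothesis 1; the one under Aim 2 is "CM group participants will have a longer sustained period of daily survey completion compared to control group participants".

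After its hypothesis sentence, Outcome Measures assigns independent t-tests to the comparison of the two outcomes. Table 4 describes each of them as a primary outcome.

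Under Effect Size Estimation, "The major goal of this Stage I pilot RCT is to estimate the effect size of the primary outcome variables", computed from the group means and variances on those variables. A single estimated effect size is then said to feed the planning of a larger trial. Aim 5 is likewise singular: "Estimate effect-size to be used to perform power analyses and sample size calculations as part of the design of a larger RCT".

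No section says whether both tests must succeed, one is enough, or each stands alone. None mentions multiplicity.

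**The concern.** A prediction joined by 'and' can be read as a conjunction that fails if either half fails. On that reading the Introduction and Outcome Measures state one hypothesis needing both results, whereas the Aims state two that can succeed or fail separately. The readings part company when exactly one test is significant, and an author could then choose the more favourable wording after seeing the data.

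A split is plausible because the outcomes penalise a missed day differently. One miss in 28 days always leaves a count of 27, but the longest run falls to anywhere between 14 and 27. The 80% power under Sample Size Justification is for a single test, so it would overstate power for a joint claim. Finally, if only one effect size were carried forward, the size of the next trial could depend on which outcome supplied it.

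**Working it through.** **1. The plan's own figure.** Inputs from Sample Size Justification: two-sided α = .05, 80% power, d = .711, 32 per group, 80 recruited, 80% retained. The normal approximation gives n = 2(1.960 + 0.842)²/.711² = 15.70/.5055 = 31.05, rounded up to 32. The exact t calculation gives 32.04, with power 79.9% at 32 per group. Retention: 80 × .80 = 64 = 2 × 32. The figure reproduces, for one outcome.

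**2. Chance of a split result.** The document gives neither the correlation r between the outcomes nor an effect for the run, so r is varied and d is taken as equal on both. Results come from 100,000 simulated trials per setting, 32 per group, two-sided t-tests at .05. P(exactly one) = P(at least one) − P(both).

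| r (assumed) | both, d = .711 | at least one, d = .711 | exactly one, d = .711 | exactly one, d = .5 |
|---|---|---|---|---|
| 0 | 63.8% | 96.0% | 32.2% | 50.3% |
| .5 | 68.7% | 91.5% | 22.8% | 33.3% |
| .8 | 72.8% | 87.1% | 14.3% | 20.7% |
| .9 | 74.5% | 84.7% | 10.2% | 14.5% |
| .95 | 76.6% | 83.8% | 7.2% | 10.2% |

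Check: P(both) + P(at least one) should equal twice the single-test power. At r = 0, 63.8 + 96.0 = 159.8 = 2 × 79.9. With the 46/35 allocation and everyone analysed, exactly one test favours CM in 12.6%, 10.2% and 7.3% of trials at r = .7, .8 and .9 (d = .711), or 24.6%, 20.2% and 14.2% (d = .5).

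**3. False-positive chance with separate tests.** If independent, 1 − .95² = 9.75%. At 46/35 and r = .7/.8/.9 it is 8.4%/8.0%/7.0% in either direction. Counting only false results that favour CM, it is 4.2%/4.0%/3.6%, against 2.5% for one test. A both-required rule would not raise the error rate above that of a single test.

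**4. One missed day.** If day k of 28 is missed, the longest run is max(k − 1, 28 − k). This is 27 at k = 1 or 28, and 14 at k = 14 or 15.

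**5. Effect size carried forward.** This uses an assumed day-level model: 28 daily completions, beta-distributed personal rates with precision 1.5 or 4, control mean .5 to .7, and none or 20% stopping early. A count d near .50 goes with a run d of .41 to .69. For 80% power these need 63.8 per group (d = .50), 94.4 (d = .41) and 34.0 (d = .69). The extremes flatter the contrast. In a repeat run, 10 of 12 settings gave a run d of about .43 to .57; only a control mean of .7 with 20% stopping early went above that.

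**6. The sections side by side.** The hypothesis sentence in Outcome Measures sits between a sentence naming two primary measures and one assigning t-tests to both. Table 4 calls each measure primary, and the Aims give each its own hypothesis. This is one structure: two outcomes, two tests, two predictions. The 'and' lists the predictions. Hypothesis numbering restarts under each aim, so the repeated label is consistent. The singular effect size follows a sentence that applies it to several variables, and nothing says one estimate is to be discarded.

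**The case for a change.** The best case for a change is that two primary outcomes with no stated decision rule leave room for choice after the fact. A split is far from rare, and one sentence would close the gap at no cost. Since effect-size estimation is the declared major goal, calling the study a pilot does not by itself answer the question of which effect size plans the next trial.

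Part of this stands. The decision rule and the treatment of multiplicity are unstated, and separate testing does raise the chance of at least one false rejection above 5%. A report should therefore conclude per outcome and not claim that the primary outcome was met on the strength of one result. The single-test power also does not describe a joint claim. It is weak evidence of intent, however, because the same section says that no power analysis is provided.

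The step to a needed change does not stand. Separate hypotheses, a verdict for each outcome and an effect size for each outcome are what the Aims, the t-tests and the plural outcome variables already lead an analyst to produce. Writing them out would alter no test, estimate or sample size. The range of 34 to 94 per group comes from the extremes of a model whose inputs are not in the document. It shows that both effect sizes should be looked at, and both will be available.

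**Conclusion.** The wording does differ between sections, but no contradiction in the analysis follows. The document never makes success on both outcomes a condition, and its operative parts agree on two separate comparisons. A split result, about 7% to 32% likely at d = .711 and 32 per group for assumed correlations of .95 down to 0, would appear as support for one aim and not the other, with both results in view. The unadjusted pair of tests carries a 7.0–8.4% chance of at least one false rejection at assumed r = .7–.9, and 9.75% at most if independent. That is a fair trade-off in a Stage I pilot meant to estimate effects. These figures assume equal effects on both outcomes and approximate normality; the conclusion itself rests on the text and does not depend on them. This is loose wording and an unstated detail that analysts would fill sensibly, so no change to the plan is called for.

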### ***Sample Size Justification***

As this is a Stage I pilot study and no preliminary data are available, a power analysis is not provided. Sample size was determined by anticipating a medium effect size (.05), 80% power, alpha level=.05 (Cohen, 1988). For two-sided *t*-tests, 32 participants/group are needed. This would allow us to detect an effect size of  $d=.711$ , which falls between medium,  $d=.05$  and large,  $d=.8$  effect sizes. Recruitment of 80 subjects with 80% retention was expected to achieve this effect size.

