**Table 4**

*Outcome Measures Overview*

Name	Time Frame	Brief Description
Number of daily surveys completed	28-day daily survey period	This primary outcome is consistent with previous CM studies.
Longest period of sustained adherence to daily survey completion	28-day daily survey period	Largest number of consecutive days wherein daily surveys were completed. This primary outcome is consistent with previous CM studies.
Mean frequency of alcohol and prescription opioid use (days of use)	28-day daily survey period to follow up	Spearman's correlations between daily survey and TLFB data for alcohol and prescription opioid frequency (days of use) were conducted for the entire sample, the CM group, and the Co group.
Mean time to complete the daily surveys	28-day daily survey period	Daily survey completion time (the amount of time from daily survey start to finish).

Name	Time Frame	Brief Description
Mean CM app feasibility and acceptability survey ratings	Follow up	CM app satisfaction, acceptability, and feasibility survey ratings (on a 0-10 scale; administered at follow-up) based on those used in a previous RCT investigating an app developed for chronic pain patients (Jamison et al., 2017).
Self-report validity and accuracy of responses	Follow up	Ratings of how honest participants were in completing the daily survey and how much the rewards made a difference in how accurately CM participants reported information in the daily survey.

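### Two unranked primary outcomes are each tested, apparently at two-sided .05, with no hierarchy: about a 7-9% chance of some false significant difference (3.5-4.5% favouring CM) if either result counts

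*Combined protocol and SAP*

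**What the plan says.** The Outcome Measures section of the Data Analysis Plan states that "the primary outcome measures are the number of completed daily self-monitoring surveys and the longest period of sustained adherence to survey completion". Table 4 labels both as primary and defines the second as "Largest number of consecutive days wherein daily surveys were completed. This primary outcome is consistent with previous CM studies". The Aims section gives each outcome its own aim and directional hypothesis; for Aim 2 it reads "CM group participants will have a longer sustained period of daily survey completion compared to control group participants". The analysis is one test per outcome: "The number of completed daily surveys and duration of continuous daily survey completion will be compared between CM and Co groups using independent" t-tests.

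The outcome analysis text sets no significance level. The only one is in Sample Size Justification, which gives "80% power, alpha level=.05", refers to two-sided t-tests and concludes that "32 participants/group are needed".

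Effect Size Estimation says that estimating effect sizes on the primary outcome variables (plural) is the major goal, then continues in the singular: "This estimated effect-size will then be used to perform power analyses and sample size calculations". No section ranks the two outcomes, splits alpha, adjusts for multiplicity, requires both to succeed, or says which outcome's effect size goes forward.

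**The concern.** With two primary tests and no stated decision rule, a reader of the results may treat a significant difference on either outcome as a positive primary finding. The chance of at least one false significant result then exceeds the .05 on which the sample size was based. The two outcomes come from the same 28 daily records, so they are strongly correlated. That limits the inflation without removing it.

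A second gap follows from the first. Aim 5 needs an effect size for the larger trial, and two primary outcomes will produce two values of d. With no outcome named in advance, the choice could be made after both values are known.

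**Working it through.** **Inputs.** From Sample Size Justification: two-sided alpha .05, 80% power, 32 per group, detectable d = .711, 80 recruited with 80% retention. From the Randomization paragraph: 46 CM and 35 Co. From Outcome Measures: two primary outcomes with one t-test each. The correlation rho between the outcomes is not in the documents; I use .5 to .9 and check that range by simulation.

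**1. The plan's own figure.** For one two-sided t-test at .05 with 80% power and d = .711, the noncentral t gives n = 32.04 per group. With 32 per group, power is 79.9% and the detectable d is .711. Recruitment: 64 / 0.8 = 80. The plan's figure is reproduced, and it is the size for a single test at two-sided .05.

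**2. Chance of at least one false significant result.** With both nulls true, Z1 and Z2 are treated as bivariate normal with correlation rho.

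- Either direction: 1 - P(|Z1| < 1.96 and |Z2| < 1.96)
- In favour of CM: 1 - P(Z1 < 1.96 and Z2 < 1.96)

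| rho | Either direction | Favouring CM |
|---|---|---|
| single test | 5.0% | 2.5% |
| 0 | 9.75% | 4.9% |
| .5 | 9.1% | 4.5% |
| .7 | 8.4% | 4.2% |
| .8 | 7.8% | 3.9% |
| .9 | 7.0% | 3.5% |

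At rho = 0 this is 1 - 0.95² = 0.0975 and 1 - 0.975² = 0.0494. Over rho .5 to .9 the inflation is 9.1/5 = 1.8 down to 7.0/5 = 1.4 times.

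**3. Check of the assumed correlation.** I simulated 28 daily completions under the null, 20,000 trials per pattern. Individual completion probabilities were beta-distributed, with and without 20-30% drop-out, at 32/32 and at 46/35. The correlation between total surveys and longest run was .73 to .81. Each test alone rejected in 4.7-5.3% of trials. At least one rejected in 7.3-8.6%, and at least one rejected in favour of CM in 3.3-4.2%.

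**4. What control would cost.** A Bonferroni split (.025 each) needs 39 per group for 80% power at d = .711, so 78 / 0.8 = 97.5, or 98 recruited. Kept at 32 per group, power per outcome falls from 79.9% to 70.7% and the detectable d rises to .787. A fixed test order holds the family-wise error at .05 with 32 per group.

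**5. Aim 5, only if the larger d were carried forward.** Assume true d = .5 on both outcomes.

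- SE of d at 46/35 = sqrt(1/46 + 1/35 + 0.25/162) = 0.228
- Expected larger d = 0.5 + 0.228 × sqrt((1 - rho)/pi)
- At rho = .8: 0.5 + 0.228 × 0.252 = 0.56

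An expected d of about .56 sizes the next trial at 52 per group, against 64 for d = .5. At 52 per group and true d = .5, power is 71%. For rho .5 to .9 the expected larger d is .59 to .54 and power is 66% to 74%. These powers are evaluated at the expected larger d and are not averaged over its sampling distribution.

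**The case against.** The strongest reply is that no either-result-suffices rule is written down. The Aims section has two separate aims, each with its own hypothesis. If each is reported as its own conclusion, each test keeps its own .05. Both outcomes are pre-specified and appear in Table 4, so neither result can be hidden. The study is a Stage I pilot whose stated major goal is estimation. This stands as to weight: the gap is an unstated decision rule, and the inflation applies only if either result is taken as support for CM. It does not dispose of the point, because the plan does state and test efficacy hypotheses and contains no both-must-succeed rule either.

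Two stronger readings are tempting and should be resisted.

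- A reader might infer a 7-9% chance of wrongly concluding that CM works. That figure counts false differences in either direction. The hypotheses are directional, so a false conclusion in favour of CM has a chance of about 3.5-4.5%, against 2.5% for one two-sided test.
- A reader might infer that the larger trial will be undersized. Nothing says that the larger d will be carried forward. The plan covers effect sizes for both outcomes, and the singular wording may be loose drafting. The expected shift of about .06 is also only about a quarter of the standard error of .23 in a single d. Naming one outcome removes the selection problem but leaves that larger uncertainty.

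**Conclusion.** The point holds, at minor severity. The two primary outcomes are unranked, each has its own t-test, and there is no multiplicity control. That each test would use two-sided .05 is inferred from the sample size paragraph, since the analysis text sets no level. If either significant result is read as support for CM, the chance of at least one false significant difference is about 7-9% instead of 5%, or about 3.5-4.5% instead of 2.5% in favour of CM. Both ranges assume a correlation of .5-.9, which the documents do not supply and which simulated 28-day data support.

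The Aim 5 part is missing detail rather than a demonstrated bias. The sizing loss in step 5 is conditional on carrying the larger d forward, as well as on true d = .5 for both outcomes and the assumed correlation.

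**What to change.** In Outcome Measures and Table 4, state the significance level and keep the order of the Aims as a fixed sequence. Test number of daily surveys completed (Aim 1) first at two-sided .05. Test longest sustained period (Aim 2) at two-sided .05 only if Aim 1 is significant; otherwise report it as an estimate with a confidence interval.

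As a secondary clarification in Effect Size Estimation, name number of surveys completed as the outcome whose effect size will size the larger trial, and report the longest-run d alongside it.

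This takes two or three sentences, with no extra participants or data. Power for Aim 1 is unchanged. The small downside is that Aim 2 cannot be claimed when Aim 1 is not significant.

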**Co Group.** The Co group will be asked to download the DynamiCare Rewards app during the baseline visit call and to complete the same daily self-monitoring survey as the CM group, but will not be provided with incentives for completing the survey. They also will receive the same reminders to complete the daily survey as the CM group. The only difference between the CM and Co groups will be the receipt of incentives for the 28-day trial.

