**Table 3**

*Overview of Study Measures*

Measure	Baseline Survey	28-Day Monitoring Period	Follow-Up Survey
Demographic information, medical/mental health history	X		
BPI, PCS, PSEQ, HADS, PSQI	X		X
Daily self-monitoring survey (via app), daily self-monitoring survey completion time		X	
TLFB, acceptability survey, validity of responses			X

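### Pain, self-efficacy, catastrophizing, mood and sleep scores are tested only as pooled pre-post change, so common drift cannot be told apart from an effect and the arms are not compared on them

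*Combined protocol and SAP*

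**What the plan says.** The Outcome Measures section of the Data Analysis Plan, in the paragraph on secondary analyses, says that pain experience and "related variables from baseline will be compared to follow up responses for the total sample using paired" t-tests. It does not name the scales. Table 3 identifies them: the row "BPI, PCS, PSEQ, HADS, PSQI" is the only one marked at both the baseline and the follow-up survey.

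No between-arm test, change-score comparison or ANCOVA is planned for these scales. The daily pain, mood and sleep items are also pooled: "The daily survey item responses will be summarized for the overall sample using descriptive statistics".

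Elsewhere the same section does use the arms. For the primary outcomes, "The number of completed daily surveys and duration of continuous daily survey completion will be compared between CM and Co groups using independent" t-tests. Completion time and acceptability ratings are also compared by arm, and the Spearman correlations are run within each arm as well as overall.

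On what separates the arms, the Co Group paragraph says: "The only difference between the CM and Co groups will be the receipt of incentives for the 28-day trial".

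**The concern.** A paired test in the total sample asks whether the mean score moved between two surveys about 28 days apart. It has no reference group. Everyone in it used the app, was asked to self-monitor and answered the same questionnaires twice. A mean change could come from monitoring, incentives, natural course, repeat testing, regression to the mean, or selective completion of the follow-up survey. The test responds to all of these alike and in either direction.

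At stake is what a p-value from this test could be taken to mean. The Self-Monitoring section of the literature review cites improved pain and function with self-management interventions, and the follow-up survey asks how far the app helped participants cope with pain. A significant pooled change could easily be set beside those as support, and the design cannot bear that. Meanwhile the one contrast on these scores that randomisation supports, CM against Co, is not planned, although the data for it will exist.

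**Working it through.** **1. The plan's own figure.** Sample Size Justification states that "32 participants/group are needed" for two-sided t-tests at 80% power and alpha 0.05, with a detectable d of .711, from 80 recruits at 80% retention. Noncentral-t power gives a detectable d of 0.7115 at 32 per group, and 0.80 × 80 = 64 = 2 × 32. The figures reproduce. They concern two-sample tests; the plan gives no calculation for the paired tests.

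**2. Inputs.**
- Completers: 64 from the plan's 80 recruits. The allocation in the Randomization paragraph (46 CM, 35 Co; 81 in all) gives 0.80 × 81 ≈ 65, split 0.80 × 46 ≈ 37 and 0.80 × 35 = 28 if retention is equal by arm.
- Baseline-to-follow-up correlation r: not in the documents. Assumed 0.5 to 0.7, with equal SD at both times.
- Drift common to both arms: not in the documents. Shown at 0.1, 0.2 and 0.3 baseline SD.

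**3. Pooled paired test under common drift, with no arm effect.** In baseline SD units, the SD of change is √(2(1 − r)), the SE of mean change is √(2(1 − r)/64), and the standardised change is dz = drift/√(2(1 − r)).

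| r | SE of mean change | drift 0.1 SD | drift 0.2 SD | drift 0.3 SD |
|---|---|---|---|---|
| 0.5 | 0.125 | 12% | 35% | 66% |
| 0.7 | 0.097 | 17% | 53% | 86% |

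Entries are the probability of two-sided p < 0.05. For example, at r = 0.7 and drift 0.3, dz = 0.3/√0.6 = 0.387, which gives 86%. With 65 completers each entry rises by at most one percentage point (86% becomes 87%).

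**4. Baseline-adjusted arm comparison under the same drift.** In a simulation with 32 per arm, r = 0.7, no arm effect and 4,000 runs per setting, ANCOVA rejected in 4.9%, 5.5% and 4.7% of runs at common drift 0, 0.2 and 0.3 SD. The paired test in the same runs rejected in 4.9%, 53.0% and 86.3%. A shift shared by both arms cancels in the arm contrast.

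**5. Precision of that comparison.** SE = √((1 − r²)(1/37 + 1/28)). At r = 0.5 this is √(0.75 × 0.0627) = 0.217 SD; at r = 0.7 it is √(0.51 × 0.0627) = 0.179 SD. The 95% half-widths are about 2.0 × SE = 0.43 and 0.36 SD. The detectable difference at 80% power is 0.713 × √(1 − r²) = 0.62 and 0.51 SD.

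**6. Number of scores.** Counting BPI severity, BPI interference, PCS, PSEQ, two HADS scores and PSQI gives about seven. The plan does not define the BPI or PSQI scores, so this count is an assumption. Seven tests at 5% give 1 − 0.95⁷ = 0.30 for at least one false positive if independent, and less if positively correlated. This applies to paired tests and ANCOVAs alike.

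**The case against.** The strongest reply is that these scales are not declared outcomes. They are absent from Table 4, no aim or hypothesis covers change in them, and effect-size estimation is limited to the primary outcomes. The analysis is one sentence in a Stage I adherence pilot. That stands, and it limits the importance of the point.

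Several stronger readings are tempting and are not supported:

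- *That the trial throws away its randomised comparison.* It does so only for these scales. Both adherence outcomes, completion time and acceptability are compared by arm.
- *That baseline values go unused.* A paired test is computed from them. Only the arm label is unused.
- *That the plan will present pooled change as benefit.* It makes no such claim and does not say how a change would be interpreted. A two-sided test could equally show worsening.
- *That regression to the mean is known to be substantial.* Eligibility requires chronic pain of at least 3 months but no minimum pain score, so its size is unknown.
- *That an arm comparison would show whether monitoring helps.* Both arms monitor, so it estimates the effect of incentives only.

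It is also fair to say that the rejection rates above are power to detect a real mean shift. The paired test is valid for that, and only attribution is in doubt. The rates depend heavily on the drift chosen: at 0.1 SD they are modest. Finally, a detectable difference of 0.5–0.6 SD is large for an indirect effect of survey incentives over 28 days. These points limit what the added analysis can deliver. They do not give the pooled test a reference group.

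**Conclusion.** The point holds as a secondary one. On these scales the plan provides only an uncontrolled pre-post test, which cannot distinguish an effect from drift in either direction, and it plans no estimate of the randomised contrast although both time points are collected. With about 64 completers and an assumed correlation of 0.5–0.7, the chance of a significant result from non-causal common drift runs from about 12–17% at 0.1 SD to 66–86% at 0.3 SD. Correlation and drift are both assumptions, so the range matters more than any one figure. No primary conclusion or sample-size input is affected.

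**What to change.** For each score measured at both times, add an exploratory ANCOVA of follow-up score on arm and baseline score. Report the adjusted CM–Co difference with its 95% CI, and state that it estimates the effect of incentives and not of self-monitoring. Replace the paired tests with pre-post change overall and by arm, as estimates with CIs labelled descriptive and uncontrolled, and not offered as evidence of benefit. Name the scores to be analysed, and report follow-up completion by arm, since differential completion would weaken the arm comparison.

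The cost is a few sentences in the Outcome Measures section and no new data. The downsides are wide intervals (half-width about 0.36–0.43 SD with 37 and 28 completers under the assumptions above) and a multiplicity across about seven scores that ANCOVA does not remove, which is why the results should be labelled exploratory.
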